Arm 3 (N=34): JNJ-3989 for 24 weeks + NA for 24 weeks + PegIFN- α 2a from baseline till Week 12.

- Follow-up (FU) Period (48 weeks), starting at Week 24.

At baseline, participants who meet the eligibility criteria will be randomized in a 1:1:1 ratio to Arm 1, Arm 2, or Arm 3. Randomization will be stratified by absolute HBsAg level (<1,000 IU/mL versus \geq 1,000 IU/mL) at baseline and country grouping as proxy for HBV genotype (GT) at enrollment, with 3 levels: Poland (predominantly GT-A) versus Russia (predominantly GT-D) versus all other countries (other or mixed GT prevalence)^a. Participants in Arm 2 who no longer meet the PegIFN- α 2a eligibility criteria at Week 12, based on available laboratory or clinical data, will continue JNJ-3989 and NA treatment until Week 24 without PegIFN- α 2a.

All participants will receive the last dose of JNJ-3989 at Week 24 and the last dose of PegIFN- α 2a at Week 23 (Arms 1 and 2) or Week 11 (Arm 3). They will start the FU Period after the Week 24 visit. If all of the following NA treatment completion criteria are met based on the Week 24 results, treatment with NA will be stopped at the next scheduled visit (ie, FU Week 2), otherwise NA treatment will continue during the complete FU Period:

- The participant has ALT <3x ULN, AND
- The participant has HBV DNA <60 IU/mL at Week 24 and HBV DNA <LLOQ at the previous visit, or HBV DNA <LLOQ at Week 24, AND
- The participant is HBeAg-negative, AND
- The participant has HBsAg <100 IU/mL.

Note: Participants who are close to meeting the protocol-defined NA treatment completion criteria with the Week 24 results, and do meet the criteria based on the FU Week 2 results may be allowed to stop NA at FU Week 4, after consultation with the Sponsor.

Participants who meet the protocol-defined NA treatment completion criteria based on the Week 24 or FU Week 2 results will be monitored closely during the 48-week FU Period with a study visit at least once every 4 weeks. NA treatment should be re-started in accordance with the NA re-treatment criteria (see below for more details).

Study intervention consists of:

- JNJ-3989: 200 mg subcutaneous injection every 4 weeks (Q4W)
- NA: tenofovir disoproxil (245 mg), or tenofovir alafenamide (TAF) (25 mg), or entecavir (ETV) (0.5 mg) tablets orally, daily (QD)
- PegIFN- α 2a: 180 μ g subcutaneous injection weekly (QW).

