**Table 4: Visit Windows**

Analysis phase	Target Day	Analysis time point (Week)	Analysis time point (label)	Time interval (days)
Screening	$-\infty$	-1	Screening	<0
Treatment period	1	0	Baseline	Pre-dose: 1
	15	2	Week 2	[2, 22]
	29	4	Week 4	[23, 43]
	57	8	Week 8	[44, 71]
	85	12	Week 12	[72, 92]
	99	14	Week 14	[93, 106]
	113	16	Week 16	[107, 127]
	141	20	Week 20	[128, 155]
	169	24	Week 24	[156, 183]
		Last visit in treatment period	25 a	EOT a
Follow-up	15	26	Follow-up Week 2	[1, 22]
	29	28	Follow-up Week 4	[23, 43]
	57	32	Follow-up Week 8	[44, 71]
	85	36	Follow-up Week 12	[72, 99]
	113	40	Follow-up Week 16	[100, 127]
	141	44	Follow-up Week 20	[128, 155]
	169	48	Follow-up Week 24	[156, 183]
	197	52	Follow-up Week 28	[184, 211]
	225	56	Follow-up Week 32	[212, 239]
	253	60	Follow-up Week 36	[240, 267]
	281	64	Follow-up Week 40	[268, 295]
	309	68	Follow-up Week 44	[296, 323]
	337	72	Follow-up Week 48	[324, $+\infty$ ]
	Last visit in the study	999 b	EOS b	

a End of treatment (EOT) visit will be the last post-baseline visit in treatment period.

b End of study (EOS) visit (last available data during the follow-up visit) will be the last visit in the study.

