#### **5.4.1.1.13. Virologic Breakthrough**

HBV virological breakthrough is defined as having a confirmed on-treatment HBV DNA increase by  $>1 \log_{10}$  from nadir level (lowest level reached during treatment) in participants who didn't have on-treatment HBV DNA level below the lower limit of quantification (LLOQ) or a confirmed on-treatment HBV DNA level  $>200$  IU/mL in participants who had on-treatment HBV DNA level below the lower limit of quantification (LLOQ). Confirmed HBV DNA increase/level means that the criterion should be fulfilled at 2 or more consecutive time points or at the last observed time points or at the last observed on-treatment time point. On-treatment will be defined as the time period in which the participant receives any of the study interventions (including NA).

In addition, participants who experience a virologic breakthrough followed by on-treatment biochemical flare will be evaluated.

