## **5.4.1.3. Time to Event Endpoints**

### **5.4.1.3.1. Time to First HBsAg Seroclearance**

Time to HBsAg seroclearance is defined as the number of days between the date of first study intervention intake and the date of the first occurrence of HBsAg seroclearance (i.e. the date of the first HBsAg seroclearance – the date of first study intervention intake + 1). The participants who withdrew early from the study before achieving HBsAg seroclearance or who did not achieve HBsAg seroclearance will be censored at the last available HBsAg assessment.

Time to HBsAg seroclearance will be also analyzed considering the participants who were retreated with NA before achieving HBsAg seroclearance as censored at the date of NA retreatment.

In addition, time to the first occurrence of the following events (i.e. the date of the first occurrence of the event – the date of first study intervention intake + 1) will be analyzed:

- HBsAg <100 IU/mL
- HBsAg decline  $\geq 1.0 \log_{10}$  IU/mL
- HBsAg decline  $\geq 2.0 \log_{10}$  IU/mL
- HBsAg decline  $\geq 3.0 \log_{10}$  IU/mL

Time to the first occurrence of the events above will be also analyzed considering the participants who were retreated with NA before achieving the event as censored at the date of NA retreatment.

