#### **5.4.1.3.4. Time to First Virologic Breakthrough**

Time to first HBV virologic breakthrough will be defined as the number of days between the date of first study intervention intake and the date of the first occurrence of virologic breakthrough (i.e. the date of the first virologic breakthrough [the first of the two confirmation visits] - the date of first study intervention intake +1). The participants who withdrew early from the study before experiencing virologic breakthrough or who did not experience virologic breakthrough will be censored at the last available HBV DNA assessment at or before EOT.

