#### **5.4.1.3.5. Time to First Flare**

Time to first biochemical flare (on- and off-treatment), clinical flare off-treatment, and virologic flare off-treatment will be evaluated.

Time to first on-treatment flare will be defined as the number of days between the date of first study intervention intake and the date of the first occurrence of on-treatment flare (i.e. the date of the first on-treatment flare [the first of the two confirmation visits] of each type- the date of first study intervention intake+1). The participants who withdrew early from the study before experiencing on-treatment flare or who did not experience on-treatment flare will be censored at the last available blood markers or liver enzymes assessment at or before EOT.

Time to the first off-treatment flare will be defined as the number of days between the date of last study intervention intake and the date of the first occurrence of off-treatment flare (i.e. the date of experiencing the first off-treatment flare [the first of the two confirmation visits] of each type- the date of last study intervention intake). The participants who withdrew early from the study before experiencing off-treatment flare or who did not experience off-treatment flare will be censored at the last available blood markers or liver enzymes assessment.

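### Time to virologic breakthrough and time to on-treatment flare count events during follow-up on NA but censor event-free participants at EOT, so any event after EOT takes the Kaplan-Meier incidence to 100%

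*SAP*

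**What the plan says.** **Event window.** SAP 5.4.1.1.13 makes breakthrough an on-treatment event and fixes the period: "On-treatment will be defined as the time period in which the participant receives any of the study interventions (including NA"). SAP 5.4.1.1.14 uses the same idea for biochemical flares, and off-treatment begins only once NA has been stopped too. NA outlasts Week 24 for many participants. Under the protocol synopsis, those who meet the completion criteria stop NA at the next visit, "otherwise NA treatment will continue during the complete FU Period". Protocol 6.5.2 adds participants who stop NA and later restart it.

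**Censoring window.** For breakthrough (SAP 5.4.1.3.4), a participant without the event "will be censored at the last available HBV DNA assessment at or before EOT". For flare (SAP 5.4.1.3.5), participants "who did not experience on-treatment flare will be censored at the last available blood markers or liver enzymes assessment at or before EOT". The footnote to SAP Table 4 defines the cut-off: "End of treatment (EOT) visit will be the last post-baseline visit in treatment period".

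**Estimators.** SAP 5.4.2.3 applies Kaplan-Meier cumulative incidence by arm, the log-rank test, a median with 90% CI, and a stratified Cox model to explore baseline factors.

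**Two related rules.** Off-treatment flare time is the "number of days between the date of last study intervention intake and the date of the first occurrence of off-treatment flare". SAP 5.4.1.3.1 also analyses "time to the first occurrence of the following events", one of which is HBsAg below 100 IU/mL, with no condition on the baseline value.

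**The concern.** A Kaplan-Meier estimate needs each participant to be at risk for as long as an event in that participant would be counted. Here a breakthrough or flare at, say, follow-up Week 12 on NA is an event, but a participant on NA without one at that visit left the risk set at EOT. Whether someone is at risk after EOT therefore depends on whether that person later has the event.

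Breakthrough and flares bear on safety, and SAP Table 10 sends both to the Data Review Committee at every review, including those after Week 24. If the time-to-event curves are among those outputs, one showing 100% for a single event would mislead, and between-arm comparisons would turn on whether an arm happened to have one late event.

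The two related rules raise smaller questions. If last intake means the last ever, someone who flares and then restarts NA has an origin later than the flare. And a participant who enters with HBsAg below 100 IU/mL has met that event before the clock starts.

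**Working it through.** The documents give no event rate, count or power for these endpoints, so there is no planned figure to reproduce. Event days and numbers staying on NA below are assumptions.

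**Inputs.**
- Arm size 34 (SAP 3).
- EOT at Day 169, the Week 24 target day in SAP Table 4. SAP Table 3 ends the treatment period the day before the Week 24 intake, so read literally EOT could fall earlier; the direction does not change.
- FU Week 2 = 169 + 14 = Day 183. FU Week 12 = 169 + 84 = Day 253. FU Week 48 = 169 + 336 = Day 505.

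**Formula.** Cumulative incidence = 1 − ∏(1 − d/n), with d events and n at risk at each event day.

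**One event, at Day 253, among 34.**
- SAP rule: the other 33 are censored at Day 169, so n = 1 and incidence is 1 − (1 − 1/1) = 100%. The crude proportion is 1/34 = 2.9%.
- Non-events censored at the last on-treatment assessment: if all 33 stay on NA to Day 505, n = 34 and incidence is 1/34 = 2.9%. If only 10 stay and the rest stop at Day 183, n = 11 and incidence is 1/11 = 9.1%.
- Events limited to EOT: 0%.

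**One event before EOT (Day 57) and two after (Days 225 and 337).**
- SAP rule: 1 − 33/34 = 2.9%; then 1 − (33/34)(1/2) = 51.5%; then 100%. The median becomes Day 225 although 3 of 34 had the event.
- Matched censoring, all others staying on NA: 1 − (33/34)(32/33)(31/32) = 8.8%. With 10 staying: 1 − (33/34)(11/12)(10/11) = 19.1%.
- Events limited to EOT: 2.9%.

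| Assumed event days (before EOT; after EOT) | SAP rule, final | Matched to end of on-treatment | Limited to EOT |
|---|---|---|---|
| none; 253 | 100% | 2.9% to 9.1% | 0% |
| 57; 253 | 100% | 5.9% to 11.8% | 2.9% |
| 57; 225, 337 | 100% | 8.8% to 19.1% | 2.9% |
| 57, 113; 225, 337, 421 | 100% | 14.7% to 27.6% | 5.9% |
| 57; none | 2.9% | 2.9% | 2.9% |

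Whenever there is an event after EOT, the last one has a risk set made up only of those having it, so the survival estimate falls to zero. With none, the three rules agree.

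**Could such events occur?** Yes. A participant below the LLOQ earlier on treatment who restarts NA and is still above 200 IU/mL at two consecutive visits on NA meets the wording of SAP 5.4.1.1.13. So does a confirmed rise in someone who never stopped NA.

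**Off-treatment flare origin.** Suppose NA stops at Day 183, a flare starts at Day 253, NA is then restarted, and the last intake is Day 505. Measured from the last intake ever, time is 253 − 505 = −252 days; measured from the intake that ended treatment, 253 − 183 = 70 days. SAP 5.4.2.1.14 expects this sequence, since it summarises flares followed by re-treatment. SAP 5.4.1.3.5 sets no censoring at NA restart, whereas 5.4.1.3.1 and 5.4.1.3.2 do so for HBsAg endpoints.

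**HBsAg below 100 IU/mL.** Criterion A13.1 (Protocol 5.1) admits screening values above 5 IU/mL, and SAP Table 8 has a baseline subgroup below 100. For HBV RNA and HBcrAg, SAP 5.5.1.3.1 and 5.5.1.3.2 require baseline above the threshold; 5.4.1.3.1 has no counterpart.

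**The case against.** The best reply is that the EOT cap itself shows the intended event window. SAP 5.4.1.2.1 glosses the on-treatment nadir as the first 24 weeks, SAP 5.4.1.1.4.1 assesses on-treatment seroclearance only in the intervention phase, and SAP 5.4.2 asks for graphs by analysis phase unless otherwise specified. If events were cut at EOT the curve would be sound and one clause would settle the matter.

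That may be what was meant, but the text does not say it. The breakthrough definition names NA, SAP 1.1 sets the objective over the whole study, SAP 5.4.2.1.13 summarises breakthrough by analysis phase, and SAP 5.4.2.3 specifies curves by arm from one clock with no limit on events. At best two readings are open, and for the same data they can give 0% and 100%.

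A second reply stands in full: time to breakthrough and time to flare are not protocol endpoints. The protocol lists a proportion with breakthrough and a frequency of flares. SAP 5.4.2.1.13 and 5.4.2.1.14 analyse these without this censoring rule. The affected curves are added by the SAP and carry no multiplicity adjustment. That limits the severity.

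A third reply stands in part. Negative off-treatment times arise only if last intake is read as last ever; the last intake before the off-treatment period is a natural reading. The wording allows both, and the missing censoring at restart remains either way.

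**Conclusion.** The event and censoring windows do not match for either endpoint, and nothing in the SAP reconciles them. In an arm with at least one on-treatment event after EOT, cumulative incidence ends at 100%, where matched windows would give 0% to 27.6% in the scenarios tried. Those sizes rest on assumed event days and assumed numbers staying on NA; the rise to 100% does not. Medians, log-rank tests and the exploratory Cox models use the same risk sets and share the fault. This should be fixed, but it does not threaten the trial's main conclusions.

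A reader might infer three stronger things that the documents do not support.
- That the curves are wrong whatever happens: with no on-treatment event after EOT the rule does no harm, and no event rate on continued NA is given.
- That the distortion is worst in the arm where most participants stay on NA: one late event takes any arm to 100%, however many remain on NA. More time on NA may make such an event likelier, but nothing in the documents measures that.
- That the breakthrough and flare results as a whole are unsound: the proportions and incidence summaries, and the primary endpoint, are untouched.

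The two related points are secondary, and the documents give no basis for sizing them. The baseline problem concerns the HBsAg threshold of 100 IU/mL, not the declines from baseline listed beside it.

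**What to change.** Use the same window for events and censoring in SAP 5.4.1.3.4 and 5.4.1.3.5, by one of two routes:

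- **(a)** Count events, and censor non-events, up to the last relevant assessment (HBV DNA for breakthrough, ALT/AST for flare) in the first continuous on-treatment period, NA in follow-up included. Report events during NA re-treatment separately; otherwise the breakthrough definition would still count them after the participant's period at risk had closed.
- **(b)** Limit both events and censoring to EOT, and analyse follow-up on NA separately.

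These estimate different quantities, so the SAP should say which is wanted. Route (a) suits an objective that covers the whole study, but its censoring follows NA completion, which depends on HBV DNA, HBsAg, HBeAg and ALT and so may be informative; the SAP should acknowledge this. Route (b) avoids that but leaves follow-up out of the main curve.

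In the same revision, define the off-treatment flare origin as the last intake before the off-treatment period begins, censor at NA restart, and restrict time to HBsAg below 100 IU/mL to participants with baseline HBsAg of at least 100 IU/mL.

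The cost is SAP wording and programming. No data collection, visit or sample size changes.

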#### **5.4.1.3.5. Time to First Flare**

Time to first biochemical flare (on- and off-treatment), clinical flare off-treatment, and virologic flare off-treatment will be evaluated.

Time to first on-treatment flare will be defined as the number of days between the date of first study intervention intake and the date of the first occurrence of on-treatment flare (i.e. the date of the first on-treatment flare [the first of the two confirmation visits] of each type- the date of first study intervention intake+1). The participants who withdrew early from the study before experiencing on-treatment flare or who did not experience on-treatment flare will be censored at the last available blood markers or liver enzymes assessment at or before EOT.

Time to the first off-treatment flare will be defined as the number of days between the date of last study intervention intake and the date of the first occurrence of off-treatment flare (i.e. the date of experiencing the first off-treatment flare [the first of the two confirmation visits] of each type- the date of last study intervention intake). The participants who withdrew early from the study before experiencing off-treatment flare or who did not experience off-treatment flare will be censored at the last available blood markers or liver enzymes assessment.

#### **5.4.2. Analysis Methods**

Summaries and graphs will be provided for each intervention arm and analysis phase, unless specified otherwise.

Statistical comparisons of the secondary endpoints among intervention arms will be done with no adjustment for multiplicity.

All secondary endpoints will be analyzed based on the observed case data. Additional analyses with specific imputation methods for missing data are added for selected endpoints.

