- d. Visits at follow up Week 8, 16, 20, 28, 32, 40, and 44 are optional for participants who continue NA treatment or have restarted NA treatment during the follow up period (provided that their HBV DNA and ALT values are stable) and mandatory for participants who do not continue NA treatment during the follow up period. Participants who experience

ALT/AST elevations as defined in Section 8.3.6.2, Intervention emergent ALT/AST Elevations, will be monitored on a weekly basis or more frequently until ALT and AST levels have returned to <5x ULN and HBV DNA is <20,000 IU/mL.

- e. If necessary (eg, for operational reasons), the Screening Period may be extended up to a maximum of 8 weeks in agreement with the Sponsor.
- f. Only applicable for participants of Arms 1 and 3.
- g. Only applicable for participants of Arm 2.
- h. Both the Platform Master ICF and the ISA ICF must be signed before the first study related activity.
- i. Minimum criteria for the availability of documentation supporting the eligibility criteria are described in the source documents section in Attachment 3 of the Master Protocol PLATFORMPAHPB2001. Clinical status will be checked and documented at screening and again before first dose of study intervention. If a participant's clinical status changes (including any available laboratory results or receipt of additional medical records) after screening but before the first dose of study intervention is given such that he or she no longer meets all eligibility criteria, then the participant should be excluded from participation in the study.
- j. Only applicable for Arm 2: Exclusion criterion A24 regarding contraindications to the use of PegIFN α 2a needs to be checked and documented again prior to the first dose of PegIFN α 2a on Week 12. If an Arm 2 participant's clinical status changes (including any available laboratory results or receipt of additional medical records) after randomization but before the first dose of PegIFN α 2a is administered, such that he or she meets exclusion criterion A24, then the participant will continue treatment as planned but without PegIFN α 2a (ie, JNJ 3989+NA until Week 24).

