6.5.1. NA Treatment Completion

All participants will receive the last dose of JNJ-3989 at Week 24 and the last dose of PegIFN- α 2a at Week 23 (Arms 1 and 2) or Week 11 (Arm 3). They will start the FU Period after the Week 24 visit. If all of the following NA treatment completion criteria are met based on the Week 24 results, treatment with NA will be stopped at the next scheduled visit (ie, FU Week 2):

- The participant has ALT <3x ULN, AND
- The participant has HBV DNA <60 IU/mL at Week 24 and HBV DNA <LLOQ at the previous visit, or HBV DNA <LLOQ at Week 24, AND
- The participant is HBeAg-negative, AND
- The participant has HBsAg <100 IU/mL.

Note: Participants who are close to meeting the protocol-defined NA treatment completion criteria with the Week 24 results, and do meet the criteria based on the FU Week 2 results may be allowed to stop NA at FU Week 4, after consultation with the Sponsor. In case of ALT elevation \geq 3x ULN at Week 24, the investigator must consider different potential causes of increased ALT to ensure appropriate work up and management as needed. If the ALT elevation is unrelated to HBV activity and/or <3x ULN by FU Week 2, NA completion may be considered at the discretion of the investigator and in consultation with the sponsor.

Participants who do not meet the above criteria based on the Week 24 or FU Week 2 results should continue NA treatment during the 48-week FU Period.

Participants who meet the above-mentioned NA treatment completion criteria will be monitored closely during the 48-week FU Period with a study visit at least once every 4 weeks. NA treatment should be re-started in accordance with the NA re-treatment criteria (see Section [6.5.2](#), NA Re-treatment Criteria During Follow-up, for more details).

The investigator should consider to re-start NA treatment per local standard of care at the EOS visit (Follow-up Week 48) for participants who met the NA treatment completion criteria based on the Week 24 (or FU Week 2) results, who did not re-start NA treatment during the follow-up phase, and who did not achieve and maintain HBsAg seroclearance. NA will not be provided by the sponsor after the final study visit.

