#### **5.4.2.1.4. HBsAg Cut-offs**

The cut-offs for HBsAg values and decreases from baseline will be used in separate summaries over time by intervention arm. The count and proportion of participants who meet those HBsAg thresholds during the study will be summarized descriptively by intervention arm, and analysis phase over time and displayed in graphs like bar charts and/or radar plots.

Cross-tabulations overtime of quantitative HBsAg (<LLOQ, ≥LLOQ) versus qualitative HBsAg (positive, negative), respectively, will also be presented by intervention arm.

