#### **5.4.2.1.9. HBV DNA Cut-offs**

The cut-offs for HBV DNA values will be used in separate summaries over time by intervention arm. The count and proportion of participants who meet those HBV DNA thresholds during the study will be summarized descriptively by intervention arm and analysis phase over time.

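### Seven follow-up visits are optional for participants on NA, so the SAP's observed-case by-arm HBsAg, HBV DNA and ALT summaries can zigzag, and raw arm differences can shrink, at those visits.

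*SAP*

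**What the plan says.** **Who attends.** Footnote d to the Schedule of Activities (Protocol 1.3) reads: "Visits at follow up Week 8, 16, 20, 28, 32, 40, and 44 are optional for participants who continue NA treatment or have restarted" NA, the restart case applying only while HBV DNA and ALT are stable. The same visits are "mandatory for participants who do not continue NA treatment during the follow up period". Footnote o expects visits only every 12 weeks for participants who continue or have restarted NA.

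**Who is off NA.** Protocol 6.5.1 lets NA stop only if ALT, HBV DNA and HBeAg criteria are met and "The participant has HBsAg <100 IU/mL", judged at Week 24 or, in some cases, FU Week 2.

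**What is analysed.** HBV DNA, quantitative HBsAg and liver tests are scheduled at every follow-up visit, and SAP Table 4 gives all 13 follow-up visits an analysis window. SAP 5.4.2 says "All secondary endpoints will be analyzed based on the observed case data", then that "Additional analyses with specific imputation methods for missing data are added for selected endpoints". For HBsAg, "The cut-offs for HBsAg values and decreases from baseline will be used in separate summaries over time by intervention arm" (5.4.2.1.4), and the counts "will be summarized descriptively by intervention arm, and analysis phase over time and displayed in graphs". For HBV DNA, participants meeting "those HBV DNA thresholds during the study will be summarized descriptively by intervention arm and analysis phase over time" (5.4.2.1.9). SAP 5.4.2.2.1 adds by-arm descriptive statistics and mean plots over time for HBsAg, HBeAg, HBV DNA and ALT, and an MMRM for log10 change from baseline in the first three.

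**The concern.** A by-arm, by-visit curve is readable only if each point describes the same people. Here the attending set changes with the visit: everyone at FU Weeks 2, 4, 12, 24, 36 and 48, and mainly participants off NA at the other seven. The second group is selected on HBsAg, and it differs from the first on HBV DNA because it has lost NA suppression. Participants who restart NA after a rebound may also leave the optional visits once stable.

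Proportions below cut-offs over time and change from baseline in HBsAg over time are named secondary endpoints (SAP 1.1). Table 10 also sends these summaries to the DRC at the follow-up interim analyses. A zigzag produced by the visit schedule could be taken for rebound and recovery, which is what follow-up is meant to show. An arm in which more participants stop NA would also look closer to the others at optional visits than it is.

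**Working it through.** **Visit count.** The plan gives no figure for this effect; the count it does give checks. Follow-up visits are FU Weeks 2, 4, 8, 12, 16, 20, 24, 28, 32, 36, 40, 44 and 48, which is 13. Removing the seven optional ones leaves 13 − 7 = 6 mandatory for all: FU Weeks 2, 4, 12, 24, 36 and 48.

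**Is there a rule for the seven?** The LOCF rules (SAP 5.4.2.1.1) and the additional off-NA denominators (5.4.2.1.5.2, 5.4.2.1.10) apply at FU Weeks 12, 24, 36 and 48 only. Nothing restricts or splits the whole-arm summaries at the optional visits.

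**Formula.** Let q be the share off NA, a the attendance of on-NA participants at an optional visit, and p_off and p_on the true proportions. Then

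observed proportion = [q·p_off + (1−q)·a·p_on] / [q + (1−q)·a].

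Setting a = 1 gives the whole arm. Setting a = 0 gives p_off, whatever q is. All values below are assumptions; the documents give none of them.

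**HBsAg, worked scenario.** In log10 IU/mL: baseline mean 3.5, SD 0.6; mean decline 1.2 (arm A) or 1.8 (arm B), SD 0.6; later rebound 0.4, SD 0.4; NA stopped if Week 24 HBsAg is below 2; a = 0.

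- Week 24 means are 3.5 − 1.2 = 2.3 and 3.5 − 1.8 = 1.7. The SD is √(0.6² + 0.6²) = 0.849.
- Stop shares are Φ((2 − 2.3)/0.849) = 36% and Φ((2 − 1.7)/0.849) = 64%, or about 12 and 22 of 34.
- Mandatory visits: means are 2.3 + 0.4 = 2.70 and 1.7 + 0.4 = 2.10, a difference of 0.60.
- Optional visits, using the truncated normal mean: 2.3 − 0.849 × 0.375/0.362 + 0.4 = 1.82, and 1.7 − 0.849 × 0.375/0.638 + 0.4 = 1.60, a difference of 0.22.

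| Simulated | Mandatory A / B | Optional A / B |
|---|---|---|
| Mean HBsAg (log10) | 2.70 / 2.10 | 1.82 / 1.60 |
| HBsAg <100 IU/mL | 23% / 46% | 59% / 70% |
| Mean decline from baseline (log10) | 0.80 / 1.40 | 1.24 / 1.65 |

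The gap in HBsAg <100 IU/mL goes from 23 to 11 points, and the gap in change from baseline from 0.60 to 0.41.

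**Range.** With declines set to the SAP's 50% and 80% response rates, the level difference goes from 0.34 to 0.31 (baseline mean 2.5, 98–99% stop) up to 0.68 to 0.40 (baseline mean 3.5, 69%/88% stop). In change from baseline the same scenarios give 0.34 to 0.33 and 0.68 to 0.50. If 25–50% of continuers attend (baseline 3.5, SD of decline 0.8), 0.68 falls only to 0.50–0.58.

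**HBV DNA <LLOQ.** Take p_on = 100% and p_off = 40%.

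- q = 0.3: 0.3 × 0.4 + 0.7 = 82% at mandatory visits, 40% at optional visits with a = 0.
- q = 0.6: 0.6 × 0.4 + 0.4 = 64% at mandatory visits, 40% at optional visits.
- With a = 0.25: 0.295/0.475 = 62% and 0.34/0.70 = 49%, a gap of 13.5 points against 18 at mandatory visits.

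**Does the MMRM repair it?** A random-intercept mixed model stood in for the SAP's MMRM (34 per arm; baseline 3.5; declines 1.2 vs 1.8; 36%/63% stopping). At optional visits the true difference in HBsAg change from baseline was 0.62, the raw observed-case difference 0.47 and the model estimate 0.62.

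**The case against.** The strongest case against is that this is presentation only.

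- **The main results are safe.** The primary endpoint is at Week 24. Functional and partial cure are defined at FU Weeks 12, 24, 36 and 48, and the off-treatment seroclearance and HBV DNA endpoints in the objectives are at FU Weeks 24 and 48. All are visits for everyone. This stands in full.
- **The MMRM handles change from baseline.** Attendance is driven mainly by observed Week 24 and FU Week 2 values, so a likelihood model largely corrects, and the HBsAg check agrees. This stands for HBsAg. HBV DNA was not tested, and the MMRM does not cover cut-off proportions, raw mean plots or ALT.
- **Off-NA analyses are already planned.** The SAP defines an NA reference timepoint (5.1.6), off-NA denominators, and a flare analysis in participants who stopped NA. These help, but they leave the whole-arm tables and curves at the seven visits unchanged.
- **Optional does not mean unattended, and counts will be shown.** Both are true. But footnote o anticipates 12-weekly visits for these participants, and a smaller n does not tell the reader that it was selected on the outcome.
- **Attenders are not simply responders.** Entry is allowed above 5 IU/mL, so a participant starting below 100 can meet the HBsAg part of the stop criteria with no decline. The selection is on HBsAg level, not on the 2 log10 response.

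A reader might infer that arm differences disappear at the optional visits. The documents do not support that as a general statement. With a = 0 the observed gap equals the difference in p_off, so a zero gap appears only if off-NA rates are assumed equal across arms and no continuer attends. In the HBsAg scenarios the differences shrank but remained.

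**Conclusion.** The concern holds for the raw, observed-case, by-arm descriptive outputs at FU Weeks 8, 16, 20, 28, 32, 40 and 44. Followed as written, the plan puts two differently selected populations on one curve, and no rule prevents it.

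Across the scenarios tried, the HBsAg arm difference is attenuated by about 10–65% in level and 3–35% in change from baseline. The HBV DNA <LLOQ difference can vanish only under the equal-rate, no-attendance assumption. These ranges rest on assumed NA-stop shares, attendance, variability and rebound; the direction follows from the visit rule and the stop criteria.

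It would be wrong to conclude that the trial's efficacy conclusions are at risk. The primary endpoint, functional and partial cure, and the FU Week 12, 24, 36 and 48 results are untouched, and the modelled HBsAg change from baseline is largely protected. This is a worthwhile, inexpensive correction to secondary descriptive summaries.

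**What to change.** In SAP 5.4.2, and in 5.5.2 where the same visits apply:

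1. Give whole-arm observed-case follow-up tables, plots and raw between-arm comparisons only at FU Weeks 2, 4, 12, 24, 36 and 48.
2. Show FU Weeks 8, 16, 20, 28, 32, 40 and 44 only for participants off NA at that visit, labelled as such and with the number observed. Alternatively, split the follow-up HBsAg, HBV DNA and ALT curves by NA status.
3. State that the MMRM continues to use all visits, so that valid data are not discarded.

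The cost is SAP wording and table shells; no new data or visits are needed. The downside is fewer whole-arm time points on the descriptive curves.
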